### **6.3.6. Documentation Requirements**

1. Portal image of each field of 3-D radiation therapy or orthogonal images that localize the isocenter placement of IMRT must be obtained on the first day of therapy but should not be submitted.

2. Weekly verification or orthogonal images are required to be taken, but not submitted. This verification information also can be gathered with cone-beam CT or other CT devices that are present in the treatment room.
3. Isodose plans and DVH in at least one axial, sagittal and frontal slice for each isocenter and DVHs of GTV, CTVs, and critical normal structures. All replanning needs to be documented in the same way.
4. Full QA report of planning (see section 10.2) needs a package of PDF or JPG documents including justification of contouring the whole esophagus (vocal cords to pylorus) pictured in 1cm CT slices, indicating the 60 Gy and 38 Gy isodose in clear colors, while subtracting other isodose-lines. Including a color coded to indicate DVH including PTV and GTV coverage, Lung: Dmax, Dmean, V20; Esophagus: V20, V38, V60 and Dmean, as well as spine and heart: Dmax and Dmean is essential. At least one transverse, coronal and longitudinal image with the 38 Gy and 60 Gy isodose lines in relation with the esophagus contour need to be provided in PDF or JPG files.

### **6.3.7. Compliance Criteria**

1. Variation Acceptable: Deviations of this magnitude are not desirable but are acceptable for treatment situations in which the target to critical structure geometry is challenging. The prescribed dose can cover as little as 90% of the PTV and still be a Variation Acceptable. The minimum dose within the PTV can fall to 93% of the prescribed dose. The max dose can exceed 120% of the prescribed dose, but it cannot go above 125% of that dose. The 5 cm esophageal exposure up to 60 Gy is a pre-planning estimate for risk, final planning acceptance is judged upon V60, V38.
2. Deviation Unacceptable: Dose distributions falling in this region are not acceptable, and plan modifications should be attempted to improve results. A Deviation Unacceptable occurs if any of the Variation Acceptable dose limits stated above are exceeded. Additionally, a Deviation Unacceptable is assigned if more than 1 cm of tissue outside the PTV receives  $\geq 120\%$  of the prescribed dose.

## 7. SELECTION AND WITHDRAWAL OF SUBJECTS

Approximately 60 total subjects from investigational sites in US will be enrolled to achieve approximately 55 subjects who receive a full course of GC4419 with standard chemoradiotherapy, assuming a dropout rate of 10%. Subjects appropriate for this trial will be identified by the institutional Principal Investigator (or designee) who will make a preliminary determination of the patient's eligibility for the trial in accordance with the provisions of the study protocol. Once a patient is enrolled to the study, the Sponsor or designee will assign a unique patient identification number that does not contain any Personal Health Information that will be used to reference the patient and corresponding data that is collected.

### 7.1. Subject Inclusion Criteria

Subjects are required to meet the following inclusion criteria before entering the trial:

1. Subjects scheduled to be treated with (definitive or adjuvant) radiation therapy in combination with chemotherapy once daily for pathologically-confirmed Stage 3 or post-operative Stage 2B NSCLC or limited stage SCLC
2. Treatment plan for subjects show that 5 cm of the esophagus for at least one surface, is included in the 60 Gy isodose volume. Dose volume histograms show esophagus dose exposure meet V38>30% and/or V60>20% (to ensure that there is a similar, significant risk for esophagitis among the subjects).

Note: In case the final planning shows that the contoured esophagus is close to but the 60 Gy isodose does not cover completely 5 cm, this subject may be allowed on the trial at the discretion of the principal investigator after discussion with and review by the Medical Monitor.

3. Age  $\geq$  18 years or older
4. ECOG performance status  $\leq$  2
5. Adequate hematologic function as indicated by:
  - a Absolute neutrophil counts (ANC)  $\geq$  1,500/mm^3
  - b Hemoglobin (Hgb)  $\geq$  9.0 g/dL
  - c Platelet count  $\geq$  100,000/mm^3
6. Adequate renal and liver function as indicated by:
  - a Estimated baseline creatinine clearance  $>60$  cc/min ( $CrCl = (140 - Age) \times Mass (kg) \times [0.85 \text{ if female}] / 72 \times [Serum Creatinine (mg/dL)]$ )
  - b Total bilirubin  $\leq$  1.5 x upper normal limit (ULN)
  - c Aspartate aminotransferase (AST) and alanine aminotransferase (ALT)  $\leq$  2.5 x ULN
  - d Alkaline phosphatase  $\leq$  2.5 x ULN
7. Males and females must agree to use a highly effective contraception starting at least one day prior to the first day of treatment and continuing for 30 days after the last dose of GC4419 (females) or 90 days (males)
8. Properly obtained written informed consent

## **7.2. Subject Exclusion Criteria**

Subjects will be excluded if they meet any of the following exclusion criteria:

1. Metastatic disease
2. Prior radiation therapy to the region of the study cancer or adjacent anatomical sites or more than 25% of total body marrow-bearing area (potentially interfering with chemo-tolerance)
3. Subjects not receiving chemotherapy
4. Grade 2 or greater esophagitis at baseline
5. Inability to provide information in the electronic symptom-reporting device
6. Subjects receiving approved or investigational immunotherapy, targeted therapy, hormone therapy, or biologic therapy
7. Participation in another clinical trial or use of another investigational agent within 30 days of first dose of GC4419.
8. Malignant tumors other than the current lung cancer within the last 5 years, unless treated definitively and with low risk of recurrence in the judgment of the treating investigator
9. Previous diagnosis of symptomatic pneumonitis ( $\geq$  Grade 2 CTCAE v 5.0 including immunotherapy induced pneumonitis)
10. Untreated, active infectious disease requiring systemic anti-infective therapy
11. Untreated HIV or history of hepatitis B/C (subjects who have been vaccinated for hepatitis B and do not have a history of infection are eligible)
12. Pregnant female subjects (including positive test for pregnancy); breastfeeding/lactating female subjects; female subjects of childbearing potential who are unwilling or unable to use a highly effective method of contraception as outlined in this protocol
13. Known allergies or intolerance to chemotherapy and similar platinum-containing compounds
14. Requirement for concurrent treatment with nitrates
15. Requirement for treatment with drugs other than nitrates that may, in the judgment of the treating investigator, create a risk for a precipitous decrease in blood pressure.
16. Clinically significant heart disease (eg, congestive heart failure of New York Heart Association Class 3 or 4, angina not well controlled by medication, or myocardial infarction within 6 months)

## **7.3. Rationale for Patient Population**

As noted in the background sections, the lung cancer patient population to be included in this study is expected to have a significant rate of radiation esophagitis to afford an opportunity to observe a clinically meaningful reduction in esophagitis when GC4419 is added to the regimen.

#### **7.4. Screen Failures**

A subject is considered a screen failure if the subject signs the informed consent form (ICF) but withdraws consent or is deemed ineligible prior to Day 1 investigational product administration. The reason why the subject was precluded from the clinical study will be collected. All subjects who sign the ICF for this study, including screening failures, will be entered in the case report form (CRF).

#### **7.5. Subject Withdrawal Criteria**

In accordance with the Declaration of Helsinki, a subject has the right to withdraw from the study at any time for any reason. The Investigator may also, at his/her discretion, discontinue a subject from participating in this study at any time. Additionally, study treatment may be discontinued for any of the following reasons:

- AE
- Medical requirement to administer a contra-indicated medication
- Subject non-compliance
- Subject has a confirmed positive serum pregnancy test
- Discontinuation of the study at the request of the Sponsor

The primary reason for ceasing treatment will be clearly documented in the subject's medical record and recorded on the appropriate CRF page. A subject who permanently discontinues treatment with GC4419 will not be allowed to be retreated.

If a subject discontinues study drug because of an AE or serious adverse event (SAE), every attempt should be made to keep the subject in the study and continue to perform the required study-related follow-up and procedures. If this is not possible or acceptable to the subject, the subject may be withdrawn from the study.

Subjects who withdraw consent for further administration of GC4419 should be encouraged to continue and complete their standard treatment with RT/chemotherapy and should be encouraged to continue with other study procedures, notably with esophagitis assessments as scheduled.

If a subject withdraws consent, additional details about the reasons for that decision will be sought and documented.

#### **7.6. Study and Site Closure**

Both the Sponsor and the Investigator reserve the right to terminate the study at any time. Should this be necessary, both parties will arrange discontinuation procedures. In terminating the study, the Sponsor and the Investigator will assure that adequate consideration is given to the protection of the subjects' interests.

Upon completion of the study, the monitor will conduct the following activities in conjunction with the Investigator or site staff, as appropriate:

- Return of all study data to the Sponsor (as applicable)
- Resolution of all data queries
- Accountability, reconciliation, and arrangements for all unused GC4419
- Review of site study records for completeness
- Shipment of laboratory samples (as applicable)

In addition, the Sponsor reserves the right to temporarily suspend or prematurely discontinue this study either at a single site or at all sites at any time for reasons including, but not limited to, safety or ethical issues or severe non-compliance. If the Sponsor determines such action is needed, the Sponsor will discuss this with the Investigator (including the reasons for taking such action) at that time. When feasible, the Sponsor will provide advance notification to the Investigator of the impending action prior to it taking effect.

The Sponsor will promptly inform all other investigators and/or institutions conducting the study if the study is suspended or terminated for safety reasons and will also inform the regulatory authorities of the suspension or termination of the study and the reason(s) for the action. If required by applicable regulations, the Investigator must inform the Institutional Review Board (IRB)/Independent Ethics Committee (IEC)/Research Ethics Board (REB) promptly and provide the reason for the suspension or termination. If the study is prematurely discontinued, all study data must be returned to the Sponsor.

Financial compensation to investigators and/or institutions will be in accordance with the agreement established between the Investigator and the Sponsor.

## **8. INVESTIGATIONAL PRODUCT AND TREATMENT OF SUBJECTS**

### **8.1. Concomitant Medications**

All concomitant therapies (eg, prescription and over-the-counter medications) taken by subjects from Baseline of Day 1 GC4419 until 30 days following the last GC4419 dose, RT or chemotherapy dose (ie, whichever occurs last) will be collected in the CRF. Additionally, any concomitant therapies if used to treat any serious or related AE will be recorded in the CRF.

Analgesic/narcotic medications will be captured and recorded along with other concomitant medications in the CRF. Narcotic use will be recorded from the baseline visit until 30 days following the last GC4419 dose, RT or chemotherapy dose (ie, whichever occurs last).

Antiemetic prophylaxis and hematopoietic growth factors use should be administered per ASCO guidelines.

Subjects who withdraw consent for further administration of GC4419 should be encouraged to continue and complete standard RT/chemotherapy treatment and other study procedures.

However, if a subject withdraws consent for the study or is removed from the study completely (ie, the subject is no longer participating in any study procedures or follow-up) no further data should be collected after the date of the subject's study discontinuation.

#### **8.1.1. Drug Interactions**

GC4419 is a strong inhibitor of CYP2D6.

Concomitant use of GC4419 increases the concentration of drugs that are CYP2D6 substrates, which may increase the risk of toxicities of these drugs. Avoid concomitant use of GC4419 with CYP2D6 substrates where minimal increases in concentration of the CYP2D6 substrate may lead to serious or life-threatening toxicities (substrates with a narrow therapeutic range). Such CYP2D6 substrates (Appendix 7) include certain beta blockers (eg, propranolol and metoprolol), antidepressants (eg, tricyclics), antipsychotics (eg, phenothiazines and most atypicals), and antiarrhythmics (eg, propafenone, flecainide).

In addition, concomitant use of GC4419 may decrease the concentration of active metabolites of prodrugs that require CYP2D6 for activation. Concomitant use of GC4419 with CYP2D6 prodrug substrates requiring functional CYP2D6 activity for their clinical benefit (eg, codeine, tramadol, tamoxifen) may decrease their effectiveness.

Concomitant administration of a CYP2D6-substrate drug concurrent with administration of GC4419 should be limited to cases in which the treating investigator has determined that the use of the specific CYP2D6-substrate drug is medically necessary. In such cases, the subject should be carefully observed for clinical adverse events of the CYP2D6-substrate drug, the dose of which may require reduction.

See the Investigator's Brochure for additional information.

## **8.2. Prohibited Medications**

Investigators may prescribe any concomitant medication or supportive therapy deemed necessary to provide adequate supportive care. Supportive care includes anti-emetic prophylaxis, hematopoietic growth factor use is per ASCO guidelines, systemic antibiotics, hydration to prevent renal damage etc., consistent with local standard of practice, with the following exceptions:

Prohibited medications/treatments:

- Gemcitabine
- Nitrates, phosphodiesterase type 5 (PDE 5) inhibitors (eg, sildenafil, tadalafil, or similar agents) or other drugs that in the judgment of the treating investigator could create a risk of a precipitous decrease in blood pressure are prohibited until at least 24 hours after the last dose of GC4419
- Other biologic response modifiers – except systemic hematopoietic growth factors for the management of anemia or myelosuppression
- Concurrent approved or investigational immunotherapy, targeted therapy, hormone or biologic therapy.
- Concurrent investigational agents intended to reduce mucosal toxicity of radiation therapy
- Other investigational agents

All medication restrictions end after the 4-week post-RT follow-up visit is completed unless otherwise noted.

Subjects who receive prohibited medications will not automatically be removed from the study; however, administration of a prohibited medication is a significant deviation from the protocol and must be reported to the Medical Monitor as soon as possible and the presiding IRB/IEC/REB (per institutional guidelines). The decision for study continuation or discontinuation will be made at that time on a case-by-case basis and in consideration of the clinical requirement and circumstances.

Antiemetic prophylaxis and hematopoietic growth factor use are permitted per ASCO guidelines. Following ASCO (and multinational association of supportive care in cancer [MASCC]) guidelines for the prevention and management of chemotherapy-induced nausea and vomiting (CINV) is strongly encouraged.

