#### 12.4.2. Secondary Efficacy Endpoints

- Incidence of acute severe (Grade 3-4) radiation esophagitis by the NCI-CTCAE scale (Grade 3-4) through the completion of chemoradiotherapy;

- Incidence of acute esophagitis  $\geq$  Grade 2 through 4 weeks after completion of chemoradiotherapy, using the NCI-CTCAE scale;
- Incidence of acute severe (Grade 3-4) radiation esophagitis through 4 weeks after completion of chemoradiotherapy;
- Presence of acute ( $\geq$  Grade 2) and acute severe (Grade 3-4) radiation esophagitis at evaluation 4 weeks after completion of chemoradiotherapy;
- Incidence of acute (through 90 days after radiation therapy) radiation pneumonitis,  $\geq$  Grade 2 by the NCI-CTCAE scale;
- Percentage weight change from baseline through the completion of chemoradiotherapy and 4 weeks after treatment.

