## APPENDIX 1. SCHEDULE OF ASSESSMENTS

Assessments	Screening Phase Within 28 days of RT start	Active Phase									Post Active Phase	
		Baseline RT Day 1	Wk 1 Days 2-7	Wk 2 Days 8-14	Wk 3 Days 15-21	Wk 4 Days 22-28	Wk 5 Days 29-35	Wk 6 Days 36-42	Last Day of RT or Early Term 	4 weeks from Last Day of RT (± 15 Days)	90 Days Post-RT (± 15 Days)	6, 9, 12 months post treatment (± 30 days)
Informed consent	X											
Inclusion/exclusion criteria	X	X										
Medical history 	X	X										
Complete Physical Exam	X								X	X	X	X
Height/Record BSA	X											
Symptom-directed Physical Exam						X						
Vital signs, ECOG and weight	X	X				X			X	X		
Serum pregnancy test	X											
Concomitant medications 		X	Weekdays						X	X		
Adverse Events 		X	Weekdays						X	X	X 	
Pneumonitis Assessment  : NCI-CTCAE scale, CT Scan, spirometry, and DLCO	X								X			X
Tumor assessment (Chest CT with or without contrast)	X										X	X
ECG (12-lead) 	X											
Esophagitis assessment—CTCAE 	X	X	Weekdays						X	X		
Esophagitis assessment—RTOG 	X	X	Weekdays						X	X		
Patient reported outcomes: NCI-PRO-CTCAE, NPRS 	X	X		X	X	X	X	X	X	X		
Patient-reported swallowing diary 	X	X	Daily including weekends						X	X		
Analgesic/narcotic use reporting		X	X	Weekly						X	X	
Parenteral/tube feeding use reporting			X	Weekly						X	X	
Blood draw: Lab safety tests 	X	X	X	X	X	X	X	X	X 	X		
Blood draw: PK 		X	X			X						
RT + chemotherapy parameters recorded	X	Per protocol schedule/standard regimen										
Dosing GC4419 		X	Days 2-5	Days 8-12	Days 15-19	Days 22-26	Days 29-33	Days 36-40				

BSA = Body Surface Area, CTCAE = Common Terminology Criteria for Adverse Events, DLCO = diffusing capacity of the lungs for carbon monoxide, ECG = Electrocardiogram, ECOG = Eastern Cooperative Oncology Group, NCI-PRO-CTCAE = National Cancer Institute-Patient Reported Outcome- Common Terminology Criteria for Adverse Events, NPRS = Numeric Pain Rating Scale, RT = Radiation Therapy, RTOG = Radiation Therapy Oncology Group.

- 1 If a subject ends study participation early and/or withdraws consent after first dose of GC4419, all last day of RT procedures should be completed.
- 2 Medical History should include NSCLC or SCLC cancer history including prior treatments and confirmation of histopathological diagnosis

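### Immunotherapy started between about Day 31 and Day 90 after RT is permitted but not recorded, so the descriptive 90-day radiation pneumonitis rate cannot be checked against that exposure

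*Combined protocol and SAP*

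**What the plan says.** **The bar and its end.** Section 8.2 prohibits "Concurrent approved or investigational immunotherapy, targeted therapy, hormone or biologic therapy". The nitrate and PDE5 item in the same list carries its own end time, but the immunotherapy item does not. The general rule therefore applies to it: "All medication restrictions end after the 4-week post-RT follow-up visit is completed unless otherwise noted". Section 10.7.6 and Appendix 1 place that visit at 28 ± 15 days after the last RT fraction.

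**Recording.** Section 8.1 has concomitant therapies taken from baseline "until 30 days following the last GC4419 dose, RT or chemotherapy dose (ie, whichever occurs last) will be collected in the CRF". Note 3 to Appendix 1 repeats this. The one extension is that "any concomitant therapies if used to treat any serious or related AE will be recorded in the CRF". This covers drugs given to treat an event, not a drug that may have caused it.

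**The endpoint.** Section 12.4.2 lists "Incidence of acute (through 90 days after radiation therapy) radiation pneumonitis" of Grade 2 or worse. The 90-day visit (Section 10.8.1, ± 15 days) consists of a physical examination, the pneumonitis assessment, updates to ongoing SAEs and a tumor CT. The 6-, 9- and 12-month visits (Section 10.8.2) consist of an examination and chest CT. Neither section lists subsequent anticancer therapy.

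**Attribution.** Exclusion 9 in Section 7.2 refers to pneumonitis of Grade 2 or worse by "CTCAE v 5.0 including immunotherapy induced pneumonitis", so the protocol treats immunotherapy as a cause in its own right. Section 11.4 records the relationship of an AE to GC4419, RT and chemotherapy only. Section 11.5 ends routine AE collection at the close of the 30-day follow-up period. Section 12.7.1 gives incidence with exact intervals and no rule for therapy started before the event.

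**The concern.** Three windows do not line up: when immunotherapy becomes allowed, when recording of therapy stops, and when the pneumonitis endpoint closes. A subject who starts immunotherapy on, say, Day 45 and has Grade 2 pneumonitis at the 90-day visit can be counted under an endpoint labelled radiation pneumonitis, and nothing the plan collects would show the exposure.

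The trial has a single arm, so there is no control group in which this exposure would balance out. Section 4.2 names the lung among the tissues that GC4419 might protect, so readers will look at this rate. What is at stake is whether it can be read as a radiation effect. Start dates that the CRF never collected cannot be recovered at the analysis stage.

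**Working it through.** The plan states no figure on this point, so there is none to reproduce. The check is day arithmetic, followed by a scale calculation on assumed rates.

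**1. Inputs**, in days after the last RT fraction
- v, day of the 4-week visit: 28 ± 15, so 13 to 43 (Section 10.7.6).
- R, last day of recording: 30 + L, where L is the day of the last GC4419 or chemotherapy dose if that follows RT, and L = 0 if RT is last (Section 8.1).
- E, end of the pneumonitis window: 90 (Section 12.4.2). The visit itself may fall on Day 75 to 105 (Section 10.8.1).

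**2. Days permitted but unrecorded** = E − max(R, v). With L = 0:

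| E | v = 13 or 28 | v = 43 |
|---|---|---|
| 75 | 75 − 30 = 45 (60%) | 75 − 43 = 32 (43%) |
| 90 | 90 − 30 = 60 (67%) | 90 − 43 = 47 (52%) |
| 105 | 105 − 30 = 75 (71%) | 105 − 43 = 62 (59%) |

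**3. Permitted days are not the same as unrecorded days.** With E = 90 and L = 0:
- v = 13: 90 − 13 = 77 permitted days, of which Days 14-30 (17 days) are recorded and 60 are not.
- v = 28: 90 − 28 = 62 permitted days, of which 2 are recorded and 60 are not.
- v = 43: 90 − 43 = 47 permitted days, none of them recorded.

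**4. Chemotherapy after RT shortens the gap.** For v up to 30, the gap is 90 − (30 + L) = 60 − L days. A last dose at an assumed L = 21 leaves 39 days. At L = 60 the gap closes.

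**5. Scale.** The documents give no rates, so all three inputs are assumptions: background radiation pneumonitis p = 10-30%, share of subjects starting immunotherapy f = 25-75%, and added risk of Grade 2 or worse pneumonitis by Day 90 among starters q = 2-10%. The rise in observed incidence is (1 − p) × f × q.
- Lowest: 0.70 × 0.25 × 0.02 = 0.0035, or 0.35 points; 55 × 0.0035 = 0.2 subjects.
- Middle: 0.80 × 0.50 × 0.05 = 0.020, or 2 points; 55 × 0.020 = 1.1 subjects.
- Highest: 0.90 × 0.75 × 0.10 = 0.0675, or 6.75 points; 55 × 0.0675 = 3.7 subjects.

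These figures count every starter. The unrecorded part is smaller by the share of cases that arise in subjects who started by Day 30, and the documents do not allow that share to be estimated. The 55 is the planned number for the primary analysis; Section 12.7.1 gives this endpoint its own population.

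**6. Against sampling error.** The exact 95% interval for an illustrative 11/55 (20%) is 10.4% to 33.0%. Even the highest shift is smaller than the distance from the estimate to either limit.

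**The case against.** Several stronger readings are tempting, and the documents do not support them.

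- *Everything started after the 4-week visit goes unrecorded.* A reader might infer this from the early end of the bar. Section 8.1 still collects all concomitant therapies to Day 30 or later, so a start on Days 14-30 is captured. The 77 days are the largest permitted overlap, not the unrecorded period.
- *The two causes cannot be separated at all.* Section 10.8.1 asks the site to evaluate specifically for RT pneumonitis, which calls for the investigator's attribution. Chest CT, spirometry and DLCO are obtained, and Section 10.2 collects mean lung dose, V20 and V30. Attribution therefore has material to draw on. What is missing is a written rule and, after Day 30, the exposure data needed to check it.
- *A protective effect would be hidden, or harm suggested.* Section 5.2 asks only to evaluate pneumonitis incidence, whereas its esophagitis incidence objectives add a comparison. Section 4.3 calls the assessment descriptive, Sections 12.6.1 and 12.7.1 plan no test, and no pneumonitis benchmark is given. No planned inference can be reversed.
- *Subjects will receive immunotherapy.* The protocol permits it after the visit but nowhere says that it will be given.

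Section 12.1 also defers technical detail to a separate SAP, and neither that text nor the CRF is shown. That reservation is fair, but an SAP cannot analyse start dates that were not collected, and the topics Section 12.6.2 assigns to it concern esophagitis scores.

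These objections reduce the size and consequence of the point. They do not close the recording gap.

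**Conclusion.** The gap is real and modest. If RT is the last treatment, immunotherapy started on about Days 31-90 is allowed but not recorded: 60 of 90 days, or 47 if the 4-week visit falls on Day 43, and fewer if chemotherapy continues after RT. The reported rate of radiation pneumonitis may therefore contain immunotherapy cases, with no planned exposure data behind the investigator's attribution.

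Total contamination of 0.35 to 6.75 points (0.2 to 3.7 of 55 subjects) rests wholly on assumed uptake, risk and background rates. It is an upper bound on the share due to unrecorded starts. The effect is confined to one descriptive secondary endpoint. The primary endpoint ends with chemoradiotherapy and is untouched. This is a cheap improvement worth making, not a flaw that threatens the trial's main result.

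**What to change.** At the existing 90-day visit, add CRF fields for (a) the agent and start date of any systemic anticancer therapy begun after RT and (b) the onset date of any Grade 2 or worse pneumonitis. The second field is needed because routine AE collection stops at 30 days and the 90-day procedures do not clearly capture onset.

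Keep the overall incidence with its exact interval as the main result. Add one sensitivity row that counts only events with onset before any immunotherapy. State beside it that the row may understate radiation pneumonitis, because it drops true radiation events arising after immunotherapy starts and shortens the time at risk. Leave the treatment rules unchanged.

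With recording through the 90-day assessment, the unrecorded period up to that assessment falls from about 60 days to 0. The cost is a few CRF fields and one table row. The sensitivity estimate will have fewer events and a downward bias. No sample size or power figure changes, since the endpoint is not tested.
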